the number of patients with TBI seen at the clinical sites and given what is feasible for us to complete the study visits in the time provided through Department of Defense (DoD) grant funding.

Data Analytic Plan:

- Definition and selection of dataset: Using an Intention-to-treat (ITT) design, all randomized participants will be included and followed up as available. The per-protocol (PP) population will include all participants in the ITT population who are compliant with study treatment as defined by >70% session exposure. Baseline demographic and clinical characteristics, including time since TBI, severity, medical comorbidity, and post-concussive symptoms will be included as covariates in the ITT dataset. Pre-post intervention benefits will be assessed using both ITT and PP datasets.
- Basic exploratory analyses will first be conducted, including checking of distributional assumptions, assessment of relationships among covariates, and missing-value multiple imputations.
- Continuous variables will be described by using mean, standard deviation, median, minimum and maximum, and 95% confidence interval for parameter estimation. Graphical display (spaghetti plots) of the outcome scores will also be generated for the 4 visits (baseline, 3 months, 9 months and 12 months) by group. Category and count variables will be described using frequency or proportions.
- Analyses will be conducted using STATA 11.2 (StataCorp, Texas, 2009) or R 2.13.2(2011). All statistical tests will be judged for significance based upon a two-sided p-value of less than 0.05.

e. Early stopping rules.

- If it is deemed that the participant requires a higher level of care (inpatient hospitalization), they will be removed from the study.

8. Risks

a. Medical risks, listing all procedures, their major and minor risks and expected frequency.

We do not expect any anticipated adverse outcomes for the study participants. The risk is minimal and therefore no harm is expected to be done to participants.

Risk associated with study involvement: As this study includes research as part of standard clinical care, there is a minor risk of unintentional release of protected health information. Risks in regard to assessments are limited to boredom, fatigue, and frustration. Additionally, given the time spent outside of their homes, participants risk exposure to COVID-19.

Risk associated with magnetic resonance imaging (MRI): MRI can damage or heat implanted or worn metallic objects or jewelry. It can also interfere with the proper functioning of implanted devices (e.g., pacemakers). In the setting of TBI, increased intracranial pressure (e.g., from a subdural hematoma) would be a contraindication for lying flat in the MRI machine for an extended period of time. Lastly, the MRIs will be reviewed for incidental findings, which can be psychologically troubling or lead to need for further work-up, which can be financially, emotionally, and logistically difficult for patients.

Vulnerable Subjects: In some instances, older adults are considered a vulnerable population. There are some risks associated with driving to appointments and exposure to hospital environment.

b. Steps taken to minimize the risks.

Mitigation of risk associated with study involvement: All study personnel are trained in general principles of informed consent, confidentiality, and privacy requirements. A study team investigator will be available by cell phone to speak to staff, subjects, or prospective subjects regarding preventing harm and minimizing risk. Participants may choose to discontinue participation in any portion of the study and continue participation in other components of data collection. If the patient ever has concerns or discomfort arises, the patient may contact the study physician at any time. We have made all elements of the protocol that can be completed remotely so. We will give participants the opportunity to complete 24 longer intervention visits rather than 36 shorter to minimize exposure during travel.

Mitigation of risk associated with data storage: Quality-conscious personnel will be recruited and undergo comprehensive training and supervision to aid with adherence to ethical standards. Each member will sign a statement indicating knowledge and understanding of the above and voluntarily disclose potential conflicts of interest. De-identified information will also be used with data entered online via REDCap (<http://project-redcap.org/>). The REDCap database will be hosted and backed up on secure servers. Analytical datasets will be stored on Johns Hopkins Box (JHBox). JHBox is a secure cloud-based file sharing service which enables people to collaborate and share information within the research team. All analysis will be undertaken on JH computers. Information will be stored in locked cabinets and offices accessible to study personnel only. Individual's data collected through assessments (e.g., surveys, tests, activity) will not be shared with participating centers without the direct consent of the person.

Mitigation of risk associated with MRI: An MRI patient screening form will be completed by our research assistant at time of enrollment. The proposed study will utilize the clearance protocol currently used at the local institution. Older adults are more likely to have indication for clearance prior to MRI scan and we have developed a screening protocol with this in mind. The neuroradiologist on the study will review all MRI scans for incidental findings. Results will be given to the participant's physician if they choose. Otherwise, we will disclose the finding directly to the patient.

Mitigation of other risks associated with study procedures: All personnel involved in collecting and handling biological specimens are to follow appropriate precautionary procedures currently recommended by the Centers for Disease Control and Prevention. Shipping of specimens, if needed, will be done in compliance with federal regulations.

c. Plan for reporting unanticipated problems or study deviations.

All study personnel are trained in general principles of informed consent, confidentiality, and privacy requirements. In addition to comprehensive training and close supervision throughout the study, staff will be reminded of their duties and responsibility to participants, each other, and the public in adhering to high ethical standards in the following: interacting with participants and each other, protecting the privacy of participants and confidentiality of records, collecting accurate and reliable data, and adhering to principles for the analysis and reporting of data. The PI will be available by cell phone to speak to staff regarding preventing harm and minimizing risk. In order to preserve confidentiality, consents and contact information, which contain personal identifiers, will be stored separately from data collection assessments. All information will be stored in secured online servers and locked cabinets and offices accessible to study personnel only. The PI will communicate IRB guidelines and regulatory correspondence to staff during training and throughout the duration of the study. Any issues that violate IRB guidelines will be reported immediately to the PI in charge of the study who will resolve and report to the IRB within 10 days.

Participant identifying information will be destroyed within two years after the completion of the study. Unanticipated problems or study deviations will be reported to JHH IRB

d. Legal risks such as the risks that would be associated with breach of confidentiality.

While we do not expect any breaches, any events occurring during the study will be reported to the PI. The PI will coordinate directly with the participant if a problem requires additional care and will immediately report any problems or deviations to the IRB within 10 days. Any unanticipated problems or study deviations during data collection will also be reported by the program coordinator. The study program coordinator will be available by cell phone to speak to participants and will periodically check in with participants regarding technology package use. Any issues will be reported immediately to the PI who will resolve and report to the IRB within 10 days. There are legal risks such as risks associated with loss of data and associated breach of confidentiality. However, to mitigate these risks, study data will be stored in a secure HIPAA compliant database (REDCap) and only de-identified data will be analyzed.

e. Financial risks to the participants.

Although there are no direct financial risks, if there are abnormal MRI or other study findings, this may lead to further medical workup and financial cost.

9. Benefits

a. Description of the probable benefits for the participant and for society.

Benefits to the participant: There may or may not be benefits to subjects who participate in this study. The participant will receive a thorough neuropsychiatric evaluation and brain MRI at no charge. Participants will also have access to the study physician should they have study or non-study-related health concerns. Should the gaming intervention improve cognitive health as we hypothesize, the patient will have reaped these benefits during the study. If the control arm has interest in trying the intervention, they will also be given that opportunity after the study has convened. Based on the minimal risks of the study and potential benefits, this study has a favorable risk-benefit ratio for participants.

Benefits to society: Benefits to society will include important information that will add to the current body of knowledge on associations between TBI and ADRD. Our study will also contribute to the body of knowledge on complex motor activities as neurocognitive enhancers, for which there are very few studies despite its promise as an intervention strategy. We also hope to introduce a novel, low-risk intervention using complex motor activities in the treatment of TBI. We also customized this intervention to be appropriate for the aging population, a population which is excluded from involvement in current neurocognitive rehab treatments due to physical limitations.

10. Payment and Remuneration

a. Detail compensation for participants including possible total compensation, proposed bonus, and any proposed reductions or penalties for not completing the protocol.

Participants will receive \$70 at each evaluation (Baseline, Follow-Up, and 9-month Follow-Up). Parking is vouchered for participants. Where budget allows, the study team will make efforts to reimburse participants for travel expenses deemed to be a barrier for participation, such as use of rideshare apps.

11. Costs

- a. Detail costs of study procedure(s) or drug (s) or substance(s) to participants and identify who will pay for them.

There are no monetary costs to participants who take part in this study. All study materials, procedures, and human resources will be directly paid for by the study grant.

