- 1) Primary Objective: To determine the efficacy of a complex cognitive-motor game, Bandit (intervention), on cognition, lifestyle, independent activities of daily living (IADL), activities of daily living (ADL), psychological and physical well-being, sleep, physical activities, and social networks in patients with past TBI in comparison to a Successful Aging Program (active control).
- 2) Objective 2: To examine mechanistic brain biomarkers of ADRD prior to and following 3 months of exposure.
- 3) Objective 3: To assess durability of any observed cognitive, lifestyle, and IADL benefits 9-months post-exposure.

3. Background (briefly describe pre-clinical and clinical data, current experience with procedures, drug or device, and any other relevant information to justify the research)

Studies have shown that those with past TBI are at elevated risk for ADRD. The brain networks most impacted post-TBI, the prefrontal cortex (PFC) and the hippocampus, are also related to the pathological processes involved in ADRD. The PFC network helps with executive processes involved in the initiation, planning, coordination, and sequencing of actions toward a goal. Executive functioning is the cognitive domain found to have the strongest impact on functional outcomes after TBI. Research has also shown that loss of brain volume in the early stages of Alzheimer's disease is greater in the PFC than in other areas of the brain. The hippocampus is functionally linked to spatial navigation and memory through the consolidation of information learned as one physically moves from location to location. The hippocampus declines most precipitously with age and is further implicated in risk for dementia. These findings suggest that improving the treatment of TBI may be an important strategy for the early intervention of ADRD.

[figure not shown]
A growing body of research suggests that non-pharmacological interventions have the potential to provide powerful treatment options for those with chronic cognitive, mental and physical sequelae after TBI. Evidence shows that even moderate physical activity such as low-intensity walking improves neurocognitive health. Cognitive enrichment from various daily activities has also been found to have beneficial effects on cognition and risk for neurodegenerative disorders.

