- The Lifestyle Activity Questionnaire (LAQ) will be used to measure frequency of participation in everyday activities (e.g., cooking, reading, gardening, etc.).
- The Community Healthy Activities Model Program for Seniors (CHAMPS) questionnaire will be used to measure weekly frequency and duration of numerous lifestyle physical activities normally undertaken by older adults such as walking, housework, aerobics, and hiking.
- The Life Space Questionnaire will be used to assess the spatial extent and frequency with which older adults move within their communities over the past week.
- Early Enrichment Lifestyle Activities Questionnaire will be used to assess total and variety of cognitively enriching activities that respondents engaged in prior to adolescence.

Well-being: The following will be used to assess psychological and physical well-being.

- The Self-efficacy questionnaire will be used to measure self-efficacy in eight domains using a Likert scale.
- The Social Ties Checklist will be used to assess one's social environment and perception of social network in relation to their perceived emotional and social support.
- The Geriatric Depression Scale will be used to assess depression in older adults.
- The Satisfaction with Life Scale will be used to assess life satisfaction and includes 5 items on a 7-point Likert Scale with higher scores indicating greater life satisfaction.

- The Positive and Negative Affect Schedule will be used to assess affect and consists of two 10-item scales to assess positive and negative affect.
- The PROMIS Sleep Disturbance and PROMIS Sleep-related Impairment Questionnaires will be used to assess perceptions of sleep quality, depth, restoration, alertness, sleepiness, tiredness, and functional impairments.
- The Media and Technology Usage and Attitudes Scale will be used to assess use of technology-based media and related attitudes toward this usage.

Health Status: The following questionnaires will be administered to assess health.

- The EuroQOL 5-Domain (EQ-5D) is a six-item questionnaire to evaluate mobility, pain/discomfort, anxiety/depression, self-care, and usual activities.
- The SF-36 is a 36-item self-report questionnaire that assesses eight domains of health status.

Objective 2, Secondary Outcomes

Brain MRI DTI: DTI parameters (FA, MD, RD, AD) will be assessed in 20 predefined regions of interest (ROI) from the JHU ICBM-DTI-81 WM atlas. Mean values of each DTI parameter for each ROI will be measured.

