Brain MRI rsfMRI: rsfMRI data will be analyzed using both seed-based (by generating 6mm spheres that will be placed in regions of interest) and group independent component analysis (utilizing Group ICA Toolbox (GIFT, MIA Lab, University of New Mexico)).

Task-related fMRI: The Flanker task will be employed to assess inhibitory control in regions of the prefrontal cortex, anterior cingulate cortex and occipital cortex (Colcombe and Kramer, 2004). These regions have been associated with neural plasticity in response to a multi-modal intervention by the PI [name] (Carlson et al., 2009).

Fluid Attenuation Inversion Recovery (FLAIR): We will use a FLAIR MRI sequence which is used to detect traumatic brain lesions.

Peak Expiratory Flow (PEF): PEF will be used to assess pulmonary function. Using a peak flow meter, we will quantify PEF by asking the participant to inhale as deeply as possible and then exhale, as hard and fast as possible, into the peak flow meter. PEF is a surrogate measure of cardiorespiratory fitness. This will allow us to investigate whether the physical activity intervention improved pulmonary function and potentially cardiorespiratory fitness. Poor PEF has also been associated with increased risk of cognitive decline. Therefore, we would like to examine whether baseline PEF or changes in PEF may be related to baseline cognition or post-intervention changes in cognition.

Note: Given ongoing concerns about COVID-19 and forced expiration, we will require all participants to have received a full course of COVID-19 vaccination. This is reflected in the inclusion criteria for the study. Additionally, the PEF procedure will be completed in a clinical space with approved ventilation.

d. Statistical plan including sample size justification and interim data analysis.

Sample Size: The power calculation for this study is based on the study by Kramer et.al (2018) and our clinical experience. In the quasi-experimental pilot clinical trial of using dual-task (cognitive and physical) exercise intervention for training in cognitive function, Kramer et. al found effect sizes of 0.91 in intervention arm and 0.75 (SD=0.33) in the peddler arm for Stroop test when using Congruent Correct-Incongruent Incorrect Metric scale. The effective sample size for the proposed trial would suggest a total evaluable sample size of 66 with alpha set at 0.05. This sample estimate represents a feasible target given

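### The secondary DTI outcome is 80 overlapping results under a blanket two-sided 0.05 rule with no correction, lead measure or exploratory label; 4 chance findings are expected if each is tested and the game has no effect

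*Combined protocol and SAP*

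**What the plan says.** Section 2 words Objective 2 as "To examine mechanistic brain biomarkers of ADRD prior to and following 3 months of exposure". Section 7b makes brain volumes the primary outcome for that objective. DTI comes in section 7c under "Objective 2, Secondary Outcomes", where "DTI parameters (FA, MD, RD, AD) will be assessed in 20 predefined regions of interest (ROI) from the JHU ICBM-DTI-81 WM atlas" and "Mean values of each DTI parameter for each ROI will be measured". The unit of analysis is thus one mean per parameter per region. No global summary, lead parameter or lead region is named.

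Section 7d, Data Analytic Plan, gives a single significance rule for the trial: "All statistical tests will be judged for significance based upon a two-sided p-value of less than 0.05". It adds that "Pre-post intervention benefits will be assessed using both ITT and PP datasets". The word exploratory occurs once, for preliminary data work ("Basic exploratory analyses will first be conducted, including checking of distributional assumptions"), and is not attached to any endpoint. The plan contains no family-wise or false-discovery adjustment and no testing order, and it gives no test or model specific to DTI.

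**The concern.** A threshold of 0.05 applied separately to 80 results does not hold the error for the set at 5%. Some results below 0.05 are to be expected even if the game does nothing to white matter.

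The four parameters also share their inputs. By definition MD = (AD + 2 x RD)/3, and FA is computed from the same diffusivities. One chance fluctuation in a region can therefore cross the threshold in several parameters at once and look like corroboration.

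At stake is the secondary mechanistic evidence under Objective 2. Nothing in the plan prevents an isolated regional DTI result from being called significant when the volumetric and clinical outcomes show nothing.

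**Working it through.** **Inputs from the documents.** Four parameters and 20 regions (7c); two-sided 0.05 for all tests (7d); MRI before and after the intervention only (4b), so one pre-to-post comparison between arms per result. The plan states no error rate for the DTI family, so it has no figure of its own to reproduce.

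**Assumptions.** Each of the 80 results is compared between arms, unadjusted, with no true effect. The correlation between test statistics is not given in the documents and is varied below.

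**Step 1: number of tests.** 4 x 20 = 80.

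**Step 2: expected false positives.** 80 x 0.05 = 4.0. Expectations add whatever the dependence, so this needs no correlation assumption.

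**Step 3: at least one false positive, independent tests.** 1 - 0.95^80 = 0.983. For scale, ln(0.5)/ln(0.95) = 13.5, so about 14 effectively independent tests are enough to pass 50%.

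**Step 4: at least one, common correlation across all 80** (100,000 simulated sets of null z-statistics, cut-off 1.96). The last column is 4.0 divided by the unrounded chance, which gives the mean number of false positives in trials that have any.

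| Assumed correlation | Chance of at least one | Multiple of 5% | Mean number when any |
|---|---|---|---|
| 0 | 98% | 19.7 | 4.1 |
| 0.3 | 91% | 18.2 | 4.4 |
| 0.5 | 73% | 14.6 | 5.5 |
| 0.6 | 60% | 12.0 | 6.7 |
| 0.7 | 47% | 9.4 | 8.5 |
| 0.8 | 34% | 6.8 | 11.8 |
| 0.9 | 21% | 4.3 | 18.7 |

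The chance is 52% at 0.66 and 49% at 0.68, so it crosses 50% near 0.67. Higher correlation makes a false positive less frequent, but when one occurs it brings more with it.

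**Step 5: other dependence structures.**
- MD built from AD and RD, and FA tied to AD minus RD (assumed AD-RD correlation 0.5; assumed correlation of FA with that difference 0.9): 94%, 76%, 58% and 47% at between-region correlations of 0, 0.5, 0.7 and 0.8.
- Four parameters fully redundant, leaving 20 tests: 64%, 54%, 48% and 29% at between-region correlations of 0, 0.3, 0.4 and 0.7.

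**Step 6: after correction.** With no true effect anywhere, the false-discovery rate equals the chance of any false claim. In null simulations with an assumed 33 per arm, Benjamini-Hochberg at 5% over the 80 p-values gave about 2 to 5%.

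**Step 7: cost in power.** An isolated effect, with no other small p-values beside it, must clear the first Benjamini-Hochberg step, 0.05/80 = 0.000625. With 33 per arm (assumed), the standardised difference detectable at 80% power is (1.960 + 0.842) x sqrt(2/33) = 0.69 at 0.05, and (3.421 + 0.842) x sqrt(2/33) = 1.05 at 0.000625. A true difference of 0.69 in one comparison alone would have about 27% power. The loss is smaller where an effect shows in several parameters or regions.

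**The case against.** **The plan does not specify 80 arm comparisons.** Section 7c says the parameters are assessed and means measured, and gives no test. A 0.05 cut-off is also compatible with adjusted p-values. This stands in part: the 80 unadjusted tests are an inference from a general rule, and the figures above are conditional on it. But that rule covers every test and mentions no adjustment, so it is the only rule that governs DTI.

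**The regions are predefined and 95% confidence intervals are planned.** Predefinition prevents the choice of regions after the fact, which is worth having, but it does not control error over 80 tests. An unadjusted 95% interval normally excludes zero just when p is below 0.05, so it inherits the problem.

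**DTI is secondary.** This stands. Volumetrics are the primary outcome for Objective 2, and that objective is worded as an examination, not a test of efficacy. A reader might infer that the trial's main conclusion is at risk; the documents do not support that.

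**The correlation is unknown and probably not zero.** This stands too. A reader might infer that a false white-matter finding is more likely than not, or that the error is always at least nine times nominal. Neither holds without condition: both fail at a common correlation of 0.8, where the chance is 34%. If the four parameters were fully redundant, 50% would no longer be reached above a between-region correlation of about 0.37.

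**The gap is general.** The same sentence in 7d covers every outcome. That is so, but the DTI family can be counted from the text and repaired on its own. A reader might infer that all other secondary outcomes should become exploratory; this check offers no evidence on them.

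**Conclusion.** The point holds in conditional form. If the 80 DTI results are each compared between arms under the 0.05 rule as written, 4 false positives are expected when the game has no effect, and this figure needs no assumption about correlation. The chance of at least one runs from about 98% under independence to 21% at an assumed common correlation of 0.9. It is above one half only below about 0.67, yet at least four times the nominal 5% across that range. Assessing the results in both the ITT and the per-protocol set could add to this and is not counted here. It would go too far to say that DTI cannot separate effect from noise: the defect lies in the decision rule, not in the measurement. The consequence is confined to secondary mechanistic claims under Objective 2. The change should be made before analysis, but the primary outcomes do not depend on it.

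**What to change.** In 7c, state that the 80 region-by-parameter comparisons between arms are judged with Benjamini-Hochberg false-discovery control at 5% across all 80. Alternatively, label them exploratory, reported with estimates and 95% confidence intervals and supporting no claim about mechanism on their own. In 7d, exempt these comparisons from the unadjusted 0.05 sentence.

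A single lead DTI measure, chosen by the investigators before analysis, is an optional addition. An average over all 20 regions is one candidate, but it would dilute a regional effect, so the choice is theirs to justify.

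The cost is a few lines of SAP wording and one line of code over p-values already computed, with no new data or participants. The statistical price of the correction is lower power for an effect confined to one region. Other secondary outcomes are outside this point.
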